K	Informed consent	39
L	Data analysis	39
M	Timeline	40
M	Table-13: Time table	41
N	Budget	41
0	References	43
App A	Summary of incidence rates based on case finding methods	43
App A App B	Draft letter to blood bank medical directors	51
	UPMC Policy/Procedure Manual Honest Broker Certification Process	52
App C	Assumptions and calculations made to estimate the TRALI rate in cases and controls	62
App D	Assumptions and calculations made to estimate the TRALI rate in cases and controls Expected participating hospitals for LAPS-II: IRB, type of medical records, and	62 64
App E	difficulty in accessing records	
App F	Screening form	66
App G	Extended data collection form	69

App H	Interim Analysis	83
App I	Expert Review Log Form	84

LAPS II: A retrospective data collection study of TRALI in recipients who are transfused with blood components from well characterized donors with or without leukocyte antibodies

A. Rationale

The recently completed Leukocyte Antibody Prevalence Study (LAPS) provides the largest well characterized population of blood donors with a detailed pregnancy and transfusion history and concomitant HLA class I and II, neutrophil, and endothelial cell antibody test results. Transfused blood components from these donors provide a unique opportunity to study the relationship between potential donor risk factors and the incidence of TRALI. The availability of a consensus definition of TRALI now facilitates establishing a more precise incidence of TRALI. A retrospective data collection (referred to as look back) study of components from these donors can provide valuable new information regarding TRALI with policy implications.

The major rationale for this study, referred to as LAPS-II, is to determine if TRALI occurs more frequently from components with HLA antibodies vs. components without HLA antibodies.

Other secondary aims of the study include generating data to examine the following questions:

- 1. Does TRALI occur more frequently from components with HLA and HNA (Human Neutrophil Antigen) antibodies vs. components with HLA antibody but without HNA antibody?
- 2. Are there antibody characteristics that are correlated with a higher incidence of TRALI such as HLA class I vs. class II, antibody strength as indicated by signal intensity on the screening assay, or antibody specificity.

B Background

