F9. Long term persistence of HLA antibodies in blood donors: The above calculations require that donations made up to two years prior to the LAPS index donation will be subject to recipient record review. These calculations also assume that HLA antibody in blood donors will persist for a prolonged period. Pilot data to support this assumption were obtained on multiparous female donors at two REDS-II Centers (Norris PJ et al.). A total of 44 donors who were previously shown to have HLA antibody by lymphocytotoxicity at least 10 years previously were re-tested for HLA antibodies. 43 of these 44 (98%) donors had antibodies detected by screening Luminex assay when a new sample was collected 10 or more years after their HLA antibodies were first detected. This study involved observations that go forward ten years since the antibodies were detected. The present protocol intends to go backward in time from the index LAPS donation to perform the record review on previous donations. However, the interval for going back will be much shorter and is expected to be two years or less based on the prevalence of HLA antibodies in LAPS donors and the pilot data obtained on the number of donations made by the LAPS donors within two years prior to the index donation. To the extent possible, prior components from LAPS donors who have had a pregnancy in the two years preceding their LAPS index donation will not be selected for the record review in order to remove the possibility that the last immunizing event may have altered the type/s of antibodies in the donor. Such exclusion is permissible because the number of donors that will have an immunizing event in the past two years is expected to be low as pregnant women are deferred from blood donation during the pregnancy and for several weeks after the delivery.

F10. REDS-II center-specific numbers of blood components for record review: Each Center will be asked to identify a total of 1,295/5 = 259 antibody positive plasma rich components and 259 antibody negative plasma rich components sent to participating hospitals. Since only 50% of the distributed products will be sent to the participating hospitals, each center must identify 259 x 2 = 518 plasma rich components from antibody positive donors. Similarly, each center must identify 518 plasma rich components from antibody negative donors.

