F12A. Identification of blood components from LAPS donors: The blood center will receive notification from the coordinating center indicating which of the LAPS donors (donor-ID and BUI) and their donations require recipient record review. For purpose of this study, individuals at the blood center who are retrieving records on the LAPS donors will not be informed of the antibody status of the donors. It is possible that the blood center's other staff may have previously been informed of the antibody test results and that some leukocyte antibody donors have been identified and notified of their antibody status per the blood center's procedures. The blood center will identify all donations made by each donor: index donation + all donations after the index donation + all donations made within two years prior to the index donation. The blood center will identify all the plasma rich components made from these donations and where these components were distributed.

LAPS donor enrollment began in September 2006 and was completed in May 2007. Donations made after the index donation will be available for the study in the REDS-II database. However, plasma products from some of these subsequent donations may not have been transfused due to implementation of TRALI risk reduction programs (which preferentially manufacture transfusable plasma components from donations by male donors) in late 2007 or early 2008.

F12B. Data management of blood components from LAPS donors: The blood center will enter all the donation information and the component distribution data for each donation into a web based system developed and maintained by the Coordinating Center. The information needed will be donation date, blood unit identifier (BUI), type of component, if/where (hospital) each component was distributed to, and the date the component was distributed. Once all the data have been entered into the computer, the blood center staff will identify all blood components (i.e. plasma components, apheresis platelets, and whole blood) that are eligible for study.

F12C. Notification of hospital transfusion service regarding blood components requiring record review: The blood center staff will notify by a letter the medical director of the hospital transfusion service that the recipient record review is needed for the list of blood components. The letter will also ask the transfusion service/blood bank to determine the disposition of each

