HLA antibody positives are those donors whose samples show a normalized background ratio (NBG) of 10.8 or higher in HLA Class I antibody testing and an NBG ratio of 6.9 or higher in HLA class II antibody testing by the Luminex method. These cut-offs represent a mean + 3 standard deviations of a log transformed distribution of values in non-transfused males enrolled in LAPS-I. For purposes of this protocol, LAPS HLA antibody negative donors will be defined as having NBG ratios for both class I and class II antibodies that are less than the mean + 2 standard deviations of the non-transfused LAPS males; this equates to an NBG value of <4.6 for Class I and <3.4 for Class II. A random sample consisting of an equal number of gender and parity frequency-matched antibody negative donors will also be selected for each participating Center.

The Coordinating Center will provide the BUI for each index donation and BUI for each subsequent donation for the study and control donors. Each blood center will then identify all the components made from these donations and their distribution to the hospitals. In addition, the REDS-II Center will identify donations made by the study donor within two years prior to the index donations, components (by component type) made from such donations and the hospitals that received these components. The component distribution data will be entered into the web based screening data forms developed and maintained by the Coordinating Center.

F24B. Other activities at the Coordinating Center: Some blood components made after the index donation may not be subject to recipient record review due to the fact some of the REDS-II participating centers may already be diverting female plasma away from transfusion to the fractionation. The interval prior to the index donation may be extended to get sufficient numbers of components for recipient record review. However, the need to go back further in time for donations is likely to be negligible based on the data on HLA antibody prevalence in LAPS donors and their prior donations.

The coordinating center will review these reports to evaluate the number of plasma rich components that were distributed to the participating hospitals. If the number of components from the antibody positive LAPS donors exceeds the number needed for the study, selection criteria will be developed to choose which components will be subject to record review.

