F.26. Once a case is classified as TRALI (whether from an antibody positive or antibody negative donor), the recipients of all other components (including red cells) made from donations by the LAPS antibody positive and antibody negative study donors in the approximate three year time frame covered by the lookback study (two years backward and one year forward) will be investigated as described for high plasma volume components. The study projects a total of 40 TRALI cases (30 from HLA antibody positive high plasma volume components and 10 from HLA antibody negative high plasma volume components), of which 70% will come from transfusable plasma and 30% from apheresis platelets. Thus 28 cases will arise from components made from whole blood; assuming each of these donors gave an average of 1.5 donations per year over the 3 year time frame under investigation and assuming that 1.6 components are made from each whole blood donation, we estimate 202 blood compoents (red cells, whole bloodderived platelets, and cryoprecipitate) will require tracing and 101 recipients (assuming 50% of these units went to participating hospitals) would require chart review. In addition, there will be similar investigations for an equal number of control donors (defined as LAPS study donors whose traced components did not cause TRALI, matched to the case donors by gender and parity). Thus, a total of 202 recipients of blood components from associated donors and control donors will be followed for all five participating REDS-II Centers. This number is in addition to the 2,590 study components record review described in Table- 4.

G. Study Design Limitations and Justification

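### The F9 exclusion that protects index antibody status over earlier donations covers pregnancy only and stays at two years, though transfusion history was recorded and the look-back may be extended

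*Protocol*

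**What the plan says.** F12A defines the eligible donations as "index donation + all donations after the index donation + all donations made within two years prior to the index donation". F26 describes the whole span as "two years backward and one year forward". Donor antibody status comes from LAPS-I testing of the index donation.

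To justify carrying that status to other donations, F9 cites a pilot in which 43 of 44 donors known to be HLA-positive at least ten years earlier were still positive on retesting. F9 states the direction of that evidence itself: "This study involved observations that go forward ten years since the antibodies were detected". It accepts that the present study goes the other way in time and answers that the interval is much shorter.

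F9 then adds one exclusion, qualified as best effort: "prior components from LAPS donors who have had a pregnancy in the two years preceding their LAPS index donation will not be selected". The purpose given is to "remove the possibility that the last immunizing event may have altered the type/s of antibodies in the donor". The loss is judged acceptable because "the number of donors that will have an immunizing event in the past two years is expected to be low", and the reason offered is donor deferral around pregnancy.

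Three other places bear on this. Section A describes the LAPS-I population as "blood donors with a detailed pregnancy and transfusion history", and Section E treats both pregnancy and transfusion as relevant to leukocyte alloimmunisation. F24B says "The interval prior to the index donation may be extended to get sufficient numbers of components for recipient record review", and F11 makes a similar provision. Sections I and J contain no donor rule on immunising events.

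**The concern.** Persistence evidence supports two inferences: a donor positive at one time tends to stay positive, and a donor negative at index was probably negative before. It does not support the inference the look-back needs in the case arm, that a donor positive at index was already positive at an earlier donation. That depends on when the donor was immunised, and the F9 exclusion is the only provision that addresses it.

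The rule is narrower than its own reasoning in two respects. It names pregnancy but not transfusion, and it is fixed at two years although the look-back need not be. A smaller gap lies on the other side of index: no rule covers a control donor who is immunised after testing and donates again.

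A case unit given before immunisation carries roughly a control unit's risk, and a control unit given after immunisation carries more. Both errors pull the two TRALI rates together, and they blur the secondary objectives on antibody strength and specificity.

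**Working it through.** **Step 1. Set the rule against the window.**

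| Immunising event | Units at risk of a wrong label | Covered by F9? |
|---|---|---|
| Pregnancy within two years before index | Prior units counted as positive | Yes, as far as it can be applied |
| Transfusion within two years before index | Prior units counted as positive | No |
| Either event more than two years before index, look-back extended | Units older than the event, counted as positive | No |
| Either event after index in a negative donor | Later units counted as negative | No |

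An example of the third row, with illustrative timings: the look-back is extended to three years and a positive donor was pregnant 2.5 years before index. The exclusion does not apply, and units given between 3 and 2.5 years before index stay in as antibody-positive.

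**Step 2. Reproduce the planned power.** Inputs from Appendix D: case rate 2.32%, control rate 0.79%, 1,175 recipients per arm, one-sided 0.05 level, exact conditional test. Summing the binomial probabilities over the one-sided Fisher rejection region gives a power of 0.9002, matching the stated 90%. The same calculation gives 0.800 at 886 and 0.850 at 1,007 per arm, matching the 9.0% row of Table-12.

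**Step 3. Add mislabelling.** Let m be the share of units with the wrong label. The protocol gives no value, so m is an assumption. Each mislabelled unit is given the other arm's full rate:

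- case rate = 2.32% − m × (2.32% − 0.79%) = 2.32% − m × 1.53%
- control rate, if that arm is also affected = 0.79% + m × 1.53%

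| m | Case rate | Power, case arm only | Control rate | Power, both arms | Risk ratio, both arms |
|---|---|---|---|---|---|
| 0 | 2.32% | 0.900 | 0.79% | 0.900 | 2.94 |
| 1% | 2.30% | 0.896 | 0.81% | 0.888 | 2.86 |
| 2% | 2.29% | 0.891 | 0.82% | 0.875 | 2.79 |
| 5% | 2.24% | 0.876 | 0.87% | 0.830 | 2.59 |
| 10% | 2.17% | 0.848 | 0.94% | 0.736 | 2.30 |

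At 1% to 2% the loss is 0.4 to 0.9 points with case-arm error only, and 1.2 to 2.5 points with equal error in both arms.

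**Step 4. Supply.** F8 reports 1,399 components from 75 donors and uses 18.5 per donor, so 2,590 / 18.5 = 140 positive donors are needed. There are 879 available, so about 16% of them suffice (140 / 879).

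**The case against.** The strongest reply is that the main route is already closed. Within the planned two years, F9 removes prior units of recently pregnant donors. A reader might infer that pre-pregnancy units routinely enter the case arm; the text does not support that. Extension of the look-back is a contingency that both F11 and F24B expect not to need.

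Transfusion is probably a minor route. H3 puts HLA positivity at 1% in men and 17.2% in women. If women are transfused about as often as men and respond similarly (an assumption, not a protocol statement), at most about 1 / 17.2, or 6%, of female positives derive from transfusion at any time in life, and only some of those fall within two years of index.

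The post-index route is also limited. The forward period is about one year, pregnant donors are deferred, and F12A expects female plasma to be diverted from late 2007 or early 2008.

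A reader might also take the 74% power as the likely cost. It needs 10% error in both arms, for which the protocol gives no support. The calculation further overstates the loss for a donor already immunised by an earlier event, whose earlier units may still carry antibody.

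Two stronger remedies might be inferred. One is to keep the prior units of recently pregnant antibody-negative donors, since the donor was still negative afterwards. F9's loss there is of supply only, controls are plentiful (5,802 antibody-negative donors in Table-9), and a rule that differs by arm would weaken the comparability that gender and parity matching is meant to give. The other is to strike the best-effort qualifier; the protocol does not show that every pregnancy or transfusion is dated, so an absolute rule might not be workable.

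These replies limit the size of the problem. They do not explain why the rule stops at pregnancy and at two years when its stated reason does neither.

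**Conclusion.** The point holds as a gap in the scope of F9. Followed as written, the exclusion can leave in pre-immunisation units from donors transfused within the look-back, or from donors with either event in an extended look-back, and count them as antibody-positive. The bias is toward no difference.

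The likely size is small: at most about 2.5 points of power if up to 2% of units are mislabelled. This rests on an assumed share, on Appendix D's rates, and on each mislabelled unit taking the other arm's full rate. The documents do not support saying that the primary comparison is seriously underpowered for this reason, or that a null result would be uninterpretable. The change is worth making because it protects the exposure variable at little cost.

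**What to change.** Reword the F9 exclusion so that, as far as records allow, prior components are not selected from donors with a recorded pregnancy or transfusion within the look-back interval actually used, however long that becomes. Apply it alike to antibody-positive and antibody-negative donors. Refer to it in F11 and F24B, so that any extension of the look-back extends the exclusion as well.

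Add one sentence on the forward period: where centre records show a pregnancy or transfusion after index in an antibody-negative donor, components donated after that event are not selected.

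The cost is a short edit, a check of the LAPS-I history when components are selected, and the loss of a few components. With 879 positive donors against about 140 needed, supply should absorb it.
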